To facilitate achieving the minimum number of responses we aim for with these two surveys we will also make the EMIS and EMIS-CV available online via the University of Manchester's approved survey hosting platform. Potential survey respondents will be directed to the web surveys' online information explaining what the survey is about. If the participant wishes to complete the survey they will first be asked to answer of screening questions to confirm eligibility; for service users the questions will establish that they are 16 years or older and have experienced an episode of psychosis, for staff the screen will confirm that they have experience of working in a professional capacity with clients who have experienced

psychosis. On fulfilling these criteria the individual will proceed to the relevant survey. For service users, on completion and exit from the survey they will be offered the opportunity to send their email address to the study Project Officer to be entered into a prize draw; this will not be offered to mental health professionals. Both service users and mental health professionals will be offered the opportunity to send their email address to the Project Officer if they should wish to receive a summary of the findings at the end of the study. Email addresses for the prize draw and for receipt of study findings will be held in separate secure databases to the survey responses so that responses may not be linked to individuals.

Additionally, for the service user online survey we will broaden the eligibility for respondents: they will not have to be within 5 years of a first episode of psychosis or currently under the care of services. Experience of psychosis, having received a diagnosis of psychosis or had treatment in the past for psychosis will be acceptable.

Posters about the study and inviting service users and NHS staff to respond to the survey have been developed. Paper versions will be posted in the University of Manchester notice boards in departments where service users and staff may see them. Electronic versions of the posters will be uploaded to the Actissist 2.0 website, relevant research websites (e.g., MQ Mental Health), and linked to in project social media posts as well as other social media sites (e.g., Reddit).

Phase 3 (Months 33-36) Data analysis; dissemination; strategy and business planning.

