- (a) Phase 1: Staff from secondary care mental health services in local NHS Trusts and University of Manchester staff who provide informed consent. We shall include a range of professions with different levels of experience/expertise to ensure a range of views about the usability and functionality of the app are gathered.
- (b) Phase 2:
Full trial: i. meet ICD-10 criteria for a schizophrenia-spectrum diagnosis (ICD codes F20, F22, F23, F25, F28, F29) as confirmed by the treating clinician or Early Intervention for Psychosis Service entry criteria, operationally defined using the Positive and Negative Syndrome Scale (PANSS) and/or the psychosis transition criteria of the Comprehensive Assessment of At-Risk Mental States; ii. in contact with mental health services; iii. within 5 years from onset of first psychotic episode,

deemed by the treating clinician; iv. meet a criterion level of positive symptoms severity, indicated by a score of >3 (symptom present) on any PANSS positive item and a score of >3 (symptom present) on any PANSS negative or PANSS general items; v.. English speaking; vi. aged 16 years or older; vii. capacity and willingness to provide informed consent; viii. not currently participating in another trial.

Service user eHealth and mHealth Interest Survey (EMIS): i. experience of psychosis (within 5 years of initial episode); ii. in current contact with either an early intervention service or a secondary care mental health service; iii. English speaking; iv. aged 16 years or older; v. capacity to provide informed consent.

eHealth and mHealth Interest Survey - Clinician Version (EMIS-CV): i. experience of working with individuals experiencing early psychosis; ii. current employment in primary or secondary mental health services or the third sector (e.g. charity).

Qualitative interviews with non-participants/participants who have withdrawn: i. early psychosis (within 5 years of initial episode); ii. in current contact with either an early intervention service or a secondary care mental health service; iii. English speaking; iv. aged 16 years or older; v. capacity to provide informed consent.

Exclusion criteria.

- i) Anyone with psychosis not in contact with a NHS mental health service.
- ii. Anyone less than 16 years old at the point of recruitment.
- iii) Anyone not capable of giving informed consent.
- iv) Non-English proficient.
- v) Score <3 on all PANSS positive, negative and general items.

Withdrawals.

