- (viii) The eHealth and mHealth Interest Survey - Clinician Version (EMIS-CV) has been developed by the research team based on findings obtained in focus groups with staff working in early intervention services in the proof-of-concept trial. Staff working in both primary and secondary health care services will be asked to complete either an online or paper-based version of the EMIS-CV. The survey contains 26 questions to elicit staff perceptions of service user technology ownership and engagement and

views towards the use of digital tools for early psychosis and takes approximately 8 minutes to administer.

(Total administration time - approx. 90 minutes).

Qualitative measures.

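### The online screen for the clinician survey (EMIS-CV) does not test the two stated inclusion criteria, so staff who do not meet them can enter

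*Protocol*

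**What the plan says.** The Protocol describes entry to the EMIS-CV in two places.

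- **Inclusion criteria (2.0 Study Design).** EMIS-CV respondents need: i. "experience of working with individuals experiencing early psychosis; ii. current employment in primary or secondary mental health services or the third sector".
- **Service user and staff surveys (2.0 Study Design).** Of people who choose to complete a survey online, it says "they will first be asked to answer of screening questions to confirm eligibility". For staff, it says "for staff the screen will confirm that they have experience of working in a professional capacity with clients who have experienced" psychosis. It then says "On fulfilling these criteria the individual will proceed to the relevant survey".

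The same account of the online surveys goes on to state a deliberate widening: "Additionally, for the service user online survey we will broaden the eligibility for respondents". No matching sentence is given for staff.

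Section 3.0 Outcomes and Measures, item (viii), says what the instrument is for. It covers staff perceptions of service users' technology ownership and engagement, and "views towards the use of digital tools for early psychosis". The sample size text in 2.0 expects upwards of 300 EMIS-CV responses and aims for a representative sample. Section 6.0 Statistical Analysis plans a descriptive analysis.

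**The concern.** A screen meant to establish eligibility should test the eligibility criteria. This one tests a looser condition, and no later eligibility step is described. Two kinds of respondent could satisfy the screen but not the criteria: people who once worked with psychosis and have since left services, and people whose experience is entirely with established psychosis.

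What is at stake is whom the clinician survey describes. It is justified by the wish to see whether qualitative findings hold more widely among staff, and its subject is digital tools for early psychosis. If respondents outside the stated population are pooled with those inside it, means and percentages no longer refer cleanly to that population. The online survey is advertised openly, including through social media, so the screen is the only described check on that route.

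**Working it through.** No arithmetic applies. The figure of 300 is an anticipated count with no power or precision calculation behind it, so there is nothing to reproduce. The check is a comparison of the two texts, element by element.

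| Element | Inclusion criteria, EMIS-CV | Online staff screen |
|---|---|---|
| Type of experience | "experience of working with individuals experiencing early psychosis" | professional work with clients who have had psychosis, at any stage |
| Employment | must be current, in one of the named settings | not asked |
| Result of passing | eligible | goes on to the survey |

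1. *Stage of illness.* The criteria say early psychosis; the screen says psychosis. Everyone who meets the first criterion through professional work also passes the screen, but the reverse does not hold.
2. *Employment.* The screen asks about experience of working in a professional capacity. That covers present and past work alike. Past work is enough, and neither current employment nor its setting is tested.
3. *Declared relaxation?* The Protocol states a broadening where it intends one, and limits it to the service user online survey. For staff, the inclusion criteria still govern.
4. *Later filter?* Passing the screen leads straight to the survey. Section 6.0 describes no exclusion based on role or employer before the responses are summarised.
5. *Size.* The number affected depends on the share of responses that arrive online and the share of those that fail a criterion. Neither is given. Section 3.0 (viii) allows online or paper completion, while section 6.0 speaks of staff responses as obtained online, so even the first share is not fixed. The count could be anything from none to a material fraction of the online responses, and the document does not support a narrower range.

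**The case against.** The strongest reply is that the recruitment routes already do most of the work. The surveys are to be promoted at NHS team meetings and through Clinical Studies Officers. Section 3.0 (viii) speaks of staff working in primary and secondary health care. The posters invite NHS staff. Most respondents reached in these ways will be in post, and many will have met early psychosis. The survey is also ancillary and descriptive, with no hypothesis test resting on it.

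That stands as a reason to expect a modest effect. It does not remove the inconsistency, because an openly posted link does not enforce the intended audience and NHS employment does not imply early-psychosis experience.

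A reader might also infer more than the text supports:

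- *That ineligible staff do enter, in some stated number of the 300.* The document shows only that they can. Someone who passes a looser screen may well meet both criteria, and any percentage would be invented.
- *That ineligible responses could never be identified, because the survey is anonymous.* Anonymity prevents tracing a person. It does not prevent excluding a response on its own answers. The 26 items are not shown, so a question on role or employer may exist; what is missing is any described use of one.
- *That respondents working outside the UK breach the criteria.* The EMIS-CV criteria contain no such restriction.

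**Conclusion.** The inconsistency is real and minor. As written, the online staff screen cannot confirm the two EMIS-CV inclusion criteria: it omits the early-psychosis element of the first and the whole of the second. Respondents who do not meet them can enter and be pooled in the descriptive clinician survey.

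The conclusion rests on reading the screen as described, and on the absence of any stated later exclusion. If the questionnaire already records role, employment and early-psychosis experience, and the team intends to filter on them, a sentence saying so would meet the point. The extent cannot be quantified from the Protocol. Nothing here bears on randomisation, the PANSS primary outcome, the trial sample size or participant safety.

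**What to change.** Bring the two texts into line, in either of two ways. Which population to survey is the team's choice.

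1. **Apply the criteria.** Add two yes/no items to the online staff screen, matching the inclusion criteria as they stand: (a) has the respondent worked with people in early psychosis; (b) is the respondent currently employed in one of the named settings. Add no geographical restriction, since the criteria have none. Base the main EMIS-CV summary on those who answer yes to both.
2. **Declare a broader population.** State in the EMIS-CV inclusion criteria that online staff eligibility is wider, as is done for service users. Record the same two items, and report respondents who do not meet the present criteria separately.

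The cost is two short items in an online form and a sentence in the Protocol. Under the first option there may be slightly fewer eligible responses towards the 300. The items are best added before the online survey opens, because anonymous respondents cannot be contacted later to supply the answers.

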Actissist participants joining CARMS will sign the Actissist Consent form Appendix 2 to say that they agree for their data (which will be identifiable) to be used by CARMS. In order for CARMS to receive this data, the participant will need to also sign the corresponding item on the CARMS Consent Form Appendix 1.

Service user and staff surveys. There is limited evidence regarding UK smartphone ownership rates in individuals with early psychosis and mental health care staff and even less regarding what staff and service users actually think about receiving a smartphone app for psychosis. In qualitative studies during the proof-of-concept trial, we identified specific facilitators and barriers to use and components staff and service users would want to see in an app. However, due to the limited number of participants recruited in qualitative research, it was not possible to generalise this information to staff and service users as a whole. Therefore, two surveys have been developed in order to explore whether the findings obtained in the qualitative studies exist on a larger scale. This survey (EMIS) will be distributed to both service users in the Actissist 2.0 trial and individuals who are not participating. Therefore, a separate participant information sheet and consent form has been created for individuals not taking part in the trial. Additionally, the staff survey (EMIS-CV) will be administered to the relevant stakeholders in both primary and secondary health care service settings. Like recruitment for the full Actissist 2.0 trial, recruitment for the survey components will be facilitated through attendance at NHS team meetings and via Clinical Studies Officers. We anticipate a minimum number of 300 responses to the EMIS (including 170 trial participants) and 300 responses to the EMIS-CV.

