Objectives: complete data analysis; dissemination will occur as detailed in the communications plan (attached); develop a strategic plan encompassing an analysis of the regulatory requirements for CE Mark and IP position, and review of potential partners/licensees to market. Commercial opportunities for Actissist will include a comprehensive analysis and monitoring of the prior art throughout the project's duration, development of an appropriate IP strategy and, if necessary, a preliminary assessment of freedom to operate. Market research identifying market needs for this technology and possible business models for commercial exploitation will be conducted.

Sample size calculation.

Phase 1: Involves approx. 5 staff members of either a local NHS Trust or University of Manchester to beta-test the Actissist app for 7 days and provide feedback on the usability and functionality of the app.

Phase 2: 170 participants recruited over 19 months. 63 per group will have 80% power to detect an effect size of 0.4 (6 points on the PANSS with an SD of 15), based on a two-group t-test with a 0.05 two-sided significance level, assuming a baseline-endpoint correlation of 0.6. Allowing 20% loss to follow-up, in order to maintain 80% power we will recruit 85 patients per group (N=170). The SD, correlation and attrition rate are based on figures from Actissist 1.0. Randomisation will be 1:1, and stratified by service (early intervention vs community mental health).

Service user ehealth and mHealth Interest Survey (EMIS). We anticipate recruiting upwards of 300 participants (including 170 full trial participants) to complete the EMIS in order to obtain a representative sample.

eHealth and mHealth Interest Survey (EMIS-CV). We anticipate recruiting upwards of 300 participants to complete the EMIS-CV in order to obtain a representative sample.

Qualitative interviews with non-participants/early withdrawers. Individuals who decide not to participate, or who withdraw early from the intervention, will be invited for a one-off interview to explore their reasons for not participating. It is not possible to accurately predict the number of service users who decide to participate in this phase; however, we expect a minimum number of 5 participants.

Phase 3: N/A

Therefore, in total, we expect the sample size of the overall project to be N=605 (170 trial plus EMIS; 130 EMIS-only); 300 EMIS-CV; 5 non-participant/early withdrawal interviews).

Inclusion criteria.

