6.0 Statistical Analysis

Quantitative Data.

The quantitative data analysis will be carried out under the supervision of [name] at Kings College London. The study database is hosted on the University of Manchester's Health eResearch Centre secure server; authorised login from another university site for co-investigators is possible to remove the need for electronic transfer of data via email in password protected files. Our primary analysis will be by an intention-to-treat approach using all randomised participants and report data in line with the CONSORT 2010 Statement (Schultz et al., 2010) showing referral and attrition rates (i.e. participant flow). The primary outcome measure will be psychotic symptoms (PANSS Total Score) based on the fact that the Actissist app targets key psychosis domains and we observed a signal on PANSS total score post-treatment in our feasibility trial. Treatment effects on the primary and secondary outcomes will be estimated using standard linear regression models. No interim analysis is planned. Every effort will be made to follow up all participants in both arms for assessments, and the analysis will use, where appropriate, statistical techniques for handling missing data.

Data obtained from the EMIS and EMIS-CV will be analysed descriptively (i.e. mean scores and percentage rates of ownership and interest) by a clinical doctorate student. Additionally, the student will link trial participants' responses to the EMIS survey questionnaire to their app usage data during the intervention period and the change in their clinical outcome scores. Linking will be achieved using pseudonymised information, i.e., participants' unique study ID on the EMIS survey response form and ID on the Baseline/ 12 and 24 week time point follow up CRFs (and/or study databases for these time points) only. There will be no requirement to access files with participant identifiable information. The EMIS responses from non-trial participants and EMIS-CV responses from mental health care staff are obtained via online survey and are anonymous.

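### The EMIS survey is called representative because it will reach 300 responses, but it is a convenience sample whose online arm also drops the early-psychosis criteria

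*Protocol*

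**What the plan says.** Section 2.0, under the sample size heading, gives the reason for the EMIS target: "We anticipate recruiting upwards of 300 participants (including 170 full trial participants) to complete the EMIS in order to obtain a representative sample". The overall count in the same place is "N=605 (170 trial plus EMIS; 130 EMIS-only" respondents, plus the clinician survey and a few interviews.

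The purpose is set out in Section 2.0 under the service user and staff surveys: "There is limited evidence regarding UK smartphone ownership rates in individuals with early psychosis". The same paragraph says that the qualitative work was too small to generalise, and that the surveys explore whether its findings hold on a larger scale.

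That section recruits through NHS team meetings and Clinical Studies Officers, and adds an online version advertised on websites and "linked to in project social media posts as well as other social media sites (e.g., Reddit". For the online version, respondents are told that "they will not have to be within 5 years of a first episode of psychosis or currently under the care of services". The online screen covers only age and having experienced psychosis.

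The EMIS inclusion criteria, also in Section 2.0, require respondents to be within 5 years of the initial episode and in current contact with services.

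Section 3.0, item (vii), has trial participants complete the EMIS at the app set-up visit. Non-trial service users return it through a care coordinator or Clinical Studies Officer, with an online link as the alternative. Section 6.0 says instead: "The EMIS responses from non-trial participants and EMIS-CV responses from mental health care staff are obtained via online survey and are anonymous". It also says that the survey data "will be analysed descriptively (i.e. mean scores and percentage rates of ownership and interest", and mentions no split by recruitment route or early-psychosis status.

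**The concern.** The protocol treats the number of responses as the means to representativeness. No sampling frame, quota, weighting or precision target is given for the EMIS. The routes are also related to what the survey measures. People who volunteer for an app trial are likely to be more interested in health apps than service users in general. People who answer an online survey found through a website or social media already have internet access and some comfort with technology.

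The online version also changes the population. It admits people long past a first episode and people outside services, although the stated evidence gap concerns early psychosis. At stake is whether the published ownership and interest percentages can be read as describing UK early-psychosis service users, which is the use that the protocol announces.

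Timing matters too. Non-trial online responses are anonymous, so if route and early-psychosis status are not captured when the form is completed, they cannot be recovered later.

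**Working it through.** **1. The plan's own counts.** 170 + 130 = 300 EMIS responses. 170 + 130 + 300 + 5 = 605 overall. Both reproduce. The trial share of the EMIS is 170/300 = 56.7%, leaving 130/300 = 43.3% for all other routes.

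**2. What 300 responses deliver.** The 95% half-width for a proportion is 1.96 × √(p(1−p)/300):

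- p = 50%: 5.7 points (the maximum)
- p = 70%: 5.2 points
- p = 80%: 4.5 points

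This is sampling error only. The protocol plans no such intervals; they are a yardstick here.

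**3. Who is selected on what.**

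- *Trial entrants (170).* The trial has no ownership requirement, because Sections 2.0 and 4.0 offer a loaned, pre-loaded handset. Entrants are selected on willingness to use an app, which bears on interest rather than ownership. They meet the 5-year and in-services criteria, but must also pass a PANSS symptom threshold that the EMIS criteria do not contain.
- *Others (about 130).* Section 3.0 allows paper or online return, while Section 6.0 describes them all as online. Online answering selects on internet access, which is related to smartphone ownership but is not the same thing.
- *Eligibility.* The online text in Section 2.0 waives two criteria that the EMIS inclusion list imposes. The service user involvement text also says that participants in all phases are within 5 years of a first episode. If all 130 answer online, up to 43.3% of the sample could lie outside the target population.

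**4. Illustrative error in a pooled ownership rate.** Let d_T be the excess ownership among trial entrants over the target population, d_O the excess among online respondents, and s the online share of the 130. Then

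error = (170 × d_T + 130 × s × d_O) / 300.

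The values of d_T, d_O, s and true ownership are assumptions; none is in the documents. With d_T = 0:

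| Assumed true ownership | s | d_O (points) | Error (points) |
|---|---|---|---|
| any | 0 | any | 0 |
| 60–80% | 0.5 | 10 | 130 × 0.5 × 10 / 300 = +2.2 |
| 60–80% | 1 | 10 | 130 × 10 / 300 = +4.3 |
| 80% | 1 | 20 (all own) | 130 × 20 / 300 = +8.7 |
| 70% | 1 | 30 (all own) | 130 × 30 / 300 = +13.0 |
| 60% | 1 | 40 (all own) | 130 × 40 / 300 = +17.3 |

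If trial entrants also exceeded the population by 5 or 10 points, add 170 × 5 / 300 = 2.8 or 170 × 10 / 300 = 5.7 points. The same term applies to interest, where an excess among trial volunteers is more plausible: an assumed 10-point excess moves the pooled interest rate by 5.7 points before any online effect.

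The error can thus exceed the sampling half-width, or be nil. The widened online eligibility could move the rate either way and is not in this formula.

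**The case against.** A reader might infer that the whole sample is selected on smartphone ownership, so that the pooled rates are definitely biased upwards. The documents do not support that. Phones are loaned, so the 57% who are trial entrants are not screened on ownership. There is an NHS route with paper return, and the online version is introduced as an addition. The statement that non-trial responses are online appears once, in a paragraph about anonymity and data linkage. A web survey can be answered on a computer, so 100% ownership among online respondents is an upper case. The illustrative range starts at 0, and the wider online population could shift rates in either direction. All of this stands.

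It can also be said that the survey is descriptive and exploratory, that ownership is only one of its topics, that no confidence intervals or single pooled headline are promised, and that table splits are commonly left to an analysis plan. Trial responses carry a study ID and are already separable. These points stand too, and they keep the matter minor.

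They do not rescue the stated rationale. The protocol itself offers 300 responses as the route to representativeness, and itself sets conflicting eligibility rules. A later analysis plan could split trial from non-trial responses. It could not recover the early-psychosis status of anonymous respondents who were never asked.

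A tempting remedy is to base the early-psychosis estimate on NHS-recruited paper respondents alone. That fails. On the Section 6.0 reading the group is empty. On the Section 3.0 reading it consists of people who chose paper over an offered link, which could bias ownership downwards.

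**Conclusion.** The claim of representativeness is not supported by the design. The EMIS is a convenience sample: 170 app-trial volunteers plus about 130 others from NHS teams, an open online survey, or both. An unseparated percentage would mix early-psychosis service users with people outside that population.

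Interest rates are likely to be too high, as are ownership rates among online respondents. The documents do not fix the amount. Under the assumed scenarios (true ownership 60–80%, trial entrants at the population rate, none to all of the 130 online), the error in a pooled ownership rate runs from 0 to about +17 points. Neither the net direction nor the size of that pooled error is established as fact.

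Two pairs of statements also need reconciling: the online eligibility against the EMIS inclusion criteria and the all-phases 5-year statement, and the return route in Section 3.0 against Section 6.0. The treatment comparison on the PANSS is not touched, so the point is minor.

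**What to change.** - In the sample size text of Section 2.0, replace the representativeness rationale with a statement that the EMIS is a convenience sample drawn from trial participants, NHS-recruited service users and open online respondents.
- Reconcile the online eligibility with the EMIS inclusion criteria and the service user involvement text. Reconcile Section 3.0 with Section 6.0 on whether non-trial respondents may return paper forms.
- Record recruitment route, time since first episode (within 5 years or not) and current contact with services at collection, including in the online screen.
- Report ownership and interest by route and early-psychosis status. Base statements about early psychosis on all respondents who meet the EMIS inclusion criteria, showing trial and NHS-recruited respondents separately. Any combined figure should be labelled as a convenience-sample figure.

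The cost is one or two extra items, one further table split and smaller groups. At p = 50%, the 95% half-width is 1.96 × √(0.25/170) = 7.5 points for 170 respondents and 1.96 × √(0.25/130) = 8.6 points for 130, against 5.7 points for 300; splitting the 130 further widens it again.
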